9.4 Statistical Analyses

The Statistical analysis plans will be finalised prior to database lock and it will include a more technical and detailed description of the statistical analyses described in this section. This section is a summary of the planned statistical analyses of the most important endpoints including primary and secondary endpoints.

9.4.1 General Considerations

All personnel involved with the analysis of the study will remain blinded until database lock and protocol violations have been identified and documented. The only exception are study independent personnel who are involved in the interim analyses in Part A. Analyses will be performed by AZ or its representatives.

Nominal significance levels will be 0.05 and all tests performed will be two-sided. All confidence intervals will be 95%.

For Part A, baseline will be defined as the last non-missing value on or before the day of first dose and on or before the day of randomisation (whatever occurs first), individually for each participant and endpoint. The baseline value for safety analyses is the last non-missing value prior to administration of the first dose of IP.

In Part B, for subjects who receive first administration of IP on the day of randomisation, the baseline value for statistical analysis of safety parameters is the last non-missing value prior to the administration of the first dose of IP. For subjects where the first administration of IP takes place after the day of randomisation, the baseline is defined as relative to the day and timepoint of randomisation instead of actual day of first administration of IP.

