3.3 General Considerations

3.3.1 General Study Level Definitions

3.3.1.1 Baseline

For the Full analysis set (FAS, see Section 4.1.2.1), baseline is defined as the last non-missing value prior to or on the day of randomisation, including unscheduled assessments that occur prior to the randomisation visit, for each subject and endpoint. If administration of the first dose of investigational product should happen to occur prior to randomisation, baseline will be defined as the last non-missing value on or before the day of the first dose.

For the Safety analysis set (SAS, see Section 4.1.2.1), baseline is defined as the last non-missing value prior to or on the day of first administration of IP, including unscheduled assessments that occur prior to the first dose visit, for each subject and endpoint.

If two assessments taken at the same day qualify as baseline, the following will apply:

- If the variable is qualitative, then the worst value from a clinical perspective will be used as the baseline value.
- For KCCQ, the first assessment (value) will be used as baseline.
- For handling of cases when more than one value could qualify as baseline for any other reason, see Section 3.3.3.

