3.3.3 Handling of Scheduled and Unscheduled Visits

Unscheduled visits can be assigned to a visit window if closer to the target day than the scheduled visit or if there is no measurement from a scheduled visit in the window. If a patient has performed more than one unscheduled visit within a window, the assessment closest to the target day will be used.

In case of ties between scheduled or unscheduled visits located on different sides of the target day, the earlier assessment will be used. In case of ties located on the same side of the target day (i.e., more than one value for the same day but different time), the value with the earlier entry time will be used.

In case of two or more scheduled or unscheduled visits for assessments with the same purpose and with identical dates and times (including possibly missing times), the average value will be derived, and in case that the record is assigned for its respective analysis visit, the average value will be used for analysis. This will be done both for cases with multiple baseline values or with multiple post-baseline values with the same date and time.

In some instances, several assessments of a vital sign variable are scheduled at the same visit for different purposes, e.g., systolic blood pressure at Visit 3. In this situation, the measurement from

the assessment for only vital signs purposes would be used, unless this is missing. If it is missing, then the supine BP pre-orthostatic test measurement or the supine BP pre-6MWT would be used for the analysis (in that order).

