4.6.6 Vital Signs

4.6.6.1 Definitions and Derivations

Vital signs (supine blood pressure (BP), pulse rate and body temperature) will be performed at timepoints according to the schedule of activities in Section 1.3 of the CSP.

For baseline vital signs assessments, the following order of eCRF forms should be used.

- VS4 (if not missing),
- VS3 (if VS4 is missing),
- VS5 (if both VS4 and VS3 are missing),

If all above are missing, earlier assessments should be used.

Observations from VS7 will not be considered as baseline since this is completed post first dose of IP as per the eCRF instructions.

The same logic applies to all post-randomisation visits.

Vital signs shift from baseline will be defined based on the following categorisation:

- Systolic BP: High if ≥ 140 ; Normal if < 140 and ≥ 90 ; Low if < 90
- Diastolic BP: High if ≥ 90 ; Normal if < 90 and ≥ 60 ; Low if < 60
- Pulse rate: High if ≥ 100 ; Normal if < 100 and ≥ 50 ; Low if < 50 .

Treatment emergent abnormalities

Vital sign treatment emergent abnormalities are determined as follows:

- Systolic BP (mmHg):
 - Observed value \geq 140 and absolute increase of \geq 20 from baseline for high level.
 - Observed value $<$ 90 and absolute decrease of \geq 20 from baseline for low level.
- Diastolic BP (mmHg):
 - Observed value \geq 90 and absolute increase of \geq 10 from baseline for high level.
 - Observed value $<$ 60 and absolute decrease of \geq 10 from baseline for low level.
- Pulse rate (beats/min):
 - Observed value \geq 100 and absolute increase of \geq 20 from baseline for high level.
 - Observed value $<$ 50 and absolute decrease of \geq 20 from baseline for low level.

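### The SAP sets the Part A safety baseline by date rather than by dose, so an off-schedule post-dose Day 1 test can become baseline

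*Protocol*

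**What the plan says.** Protocol 9.4.1 gives two Part A baselines side by side. The general one works by day. The safety one works by dose: "The baseline value for safety analyses is the last non-missing value prior to administration of the first dose of IP".

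SAP 3.3.1.1 replaces the second. For the safety analysis set, "baseline is defined as the last non-missing value prior to or on the day of first administration of IP", with the added phrase "including unscheduled assessments that occur prior to the first dose visit". No condition on time relative to dosing appears. For two values on the same day it adds: "If the variable is qualitative, then the worst value from a clinical perspective will be used as the baseline value". Other ties go to SAP 3.3.3. Same-day values with different times resolve to the earlier one; for records "with identical dates and times (including possibly missing times), the average value will be derived".

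One exception is written in, for vital signs (SAP 4.6.6.1): "Observations from VS7 will not be considered as baseline since this is completed post first dose of IP".

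SAP Section 2, which lists departures from the protocol, mentions only the standard deviation assumed for KCCQ-TSS and states that nothing else changed. The SAP amendment history for version 4 confirms that dropping time from the baseline definition was intended.

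**The concern.** A safety baseline should describe the participant before exposure. The first dose is given in clinic on Day 1, so a rule that looks only at the date cannot separate a result obtained before the tablet from one obtained after it. For qualitative variables the worst-value rule then prefers the abnormal result.

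This matters most for the ECG. SAP 4.6.7.1 counts an ECG abnormality as treatment-emergent only if it is clinically significant and was absent at baseline. If a post-dose finding is itself taken as baseline, neither that finding nor its persistence at later visits counts. Under the worst-value rule the error runs in one direction, towards fewer treatment-emergent findings. The VS7 exception shows that the SAP's authors saw the issue for vital signs; no matching rule covers ECG, urinalysis or blood samples.

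**Working it through.** No sample size, power or error rate bears on this point, so the check is to apply both sets of rules to each possible Day 1 pattern.

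| Day 1 pattern | Protocol 9.4.1 baseline | SAP baseline | Agree? |
|---|---|---|---|
| Qualitative test: normal pre-dose, abnormal post-dose | Normal | Abnormal (worst value, 3.3.1.1) | No |
| Quantitative test: pre- and post-dose values, both timed | Pre-dose value | Earlier value, which is the pre-dose one (3.3.3) | Yes |
| Quantitative test: pre- and post-dose values, times missing | Pre-dose value | Average of the two (3.3.3) | No |
| Only a post-dose value on Day 1 | Last earlier value, normally screening | The post-dose value | No |
| Post-dose vital signs on VS7 | Excluded | Excluded (4.6.6.1) | Yes |

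**Which records can fall in the disagreeing rows.** Footnotes b and l of the Part A schedule (protocol 1.3) place the Visit 3 assessments and blood draws before dosing, and the first dose after all pre-dose procedures. The disagreement therefore reaches only scheduled tests done late, repeat tests, and possibly unscheduled tests on Day 1.

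**Which outputs are affected.**

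- ECG: the treatment-emergent table (SAP 4.6.7.1) and the shift from baseline to last observation (SAP 4.6.7.2). A post-dose Day 1 ECG lies in the on-treatment period, which starts on the date of first dose (SAP 3.3.1.5), yet can serve as baseline.
- Dipstick: only the urinalysis shift table (SAP 4.6.4.2). Treatment-emergent urinalysis abnormalities are defined for quantitative parameters (SAP 4.6.4.1), which the worst-value rule does not cover.
- Blood chemistry and haematology: change from baseline, and the requirement that an abnormality be more extreme than baseline (SAP 4.6.3.1), through the averaging and lone-value rows.

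I could not read the ECG row of the Part A schedule, so a scheduled pre-dose ECG at Visit 3 is inferred. If there is none, a post-dose Day 1 ECG falls in the lone-value row and displaces screening; the conflict remains.

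**Size.** The documents give no count of off-schedule Day 1 tests. Purely as an assumption, 1% to 3% of 660 participants would be 660 × 0.01 = 6.6 to 660 × 0.03 = 19.8, or about 7 to 20. That counts participants exposed to the rule, not misclassified findings. Zero is also compatible with the documents.

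**The case against.** The strongest reply is that the SAP already protects nearly all the data. Planned Visit 3 tests are pre-dose. The one post-dose Day 1 assessment that the documents identify, the former post-dose orthostatic and vital-signs assessment, is kept out of baseline through VS7, and SAP 3.3.2 sends VS7 data to the Week 4 window. The phrase "including unscheduled assessments that occur prior to the first dose visit" can also be read as admitting unscheduled tests only if they precede the dosing visit. Most of this stands. However, the phrase states what is included and does not expressly exclude later same-day tests. Nor does it reach a scheduled Visit 3 test performed late.

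Four stronger readings are tempting and are not supported:

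- *Any value dated on the day of first dose can become baseline.* VS7 is barred and timed quantitative pairs resolve to the earlier value.
- *A post-dose finding is never counted.* Adverse events are collected from the first dose, clinically relevant deteriorations are reportable as adverse events (protocol 8.3.1 and 8.3.5), and ECGs and laboratory values are listed individually.
- *Dipstick findings vanish from the treatment-emergent table.* A qualitative dipstick result does not enter that table.
- *The rule hides drug effects in a known number of participants.* It applies equally to placebo, and the documents supply no number.

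**Conclusion.** The protocol and SAP definitions conflict, the SAP does not declare the departure, and in three of the five patterns above the two give different baselines. The consequence is narrow: descriptive Part A safety tables, for late, repeat or unscheduled Day 1 tests. The clearest case is a clinically significant post-dose ECG that becomes baseline and is omitted from the treatment-emergent and shift tables. No efficacy result is touched.

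The number of affected records is unknown and probably small. This rests on two assumptions: that sites followed the pre-dose order at Visit 3, and that the clause on unscheduled assessments is not programmed as an exclusion. If it is programmed that way, unscheduled tests drop out and only scheduled tests done late, or scheduled tests repeated, remain. The point is minor, but the correction restores the protocol's own rule.

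**What to change.** In SAP 3.3.1.1, for the safety analysis set:

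1. Restore the protocol definition: the last non-missing value before the first dose is administered.
2. Treat scheduled Visit 3 assessments as pre-dose unless they are recorded as taken after dosing.
3. Do not use an unscheduled Day 1 assessment as baseline unless it is shown to be pre-dose.
4. Apply the worst-value rule, and the averaging rule in SAP 3.3.3, only among pre-dose values.

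If the date-only rule is kept on purpose, declare it in SAP Section 2 as a departure from protocol 9.4.1.

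The cost is a wording change and a derivation flag. A few baselines would revert to the screening value. A convention is needed where assessment time is not recorded; the SAP's ECG listing mentions only the date, so ECG may be such a case. Items 2 and 3 supply that convention.

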9.4.2 Efficacy

9.4.2.1 Primary Endpoint(s)

The primary efficacy endpoints are KCCQ-TSS and 6MWD and the primary efficacy variables are change from baseline in KCCQ-TSS and 6MWD at 16 weeks for Part A and at 24 weeks for Part B.

All primary variables will be analysed using ANCOVA with baseline and treatment group as covariate, and will be adjusted for the stratification factor for neutrophil count (Part A and Part B), comparing the AZD4831 doses versus placebo. For Part A, both single doses alone, and both doses pooled, will be compared with placebo. In Part B, a term for treatment by-baseline interaction will be included as independent variable in the model for KCCQ-TSS.

Model summary in Part A:

- 6MWD change from baseline at 16 Weeks:

$$\begin{aligned} E[CHG_{6MWD} | BASE_{6MWD}, TRT] \\ = \beta_0 + \beta_1 * BASE_{6MWD} + \beta_2 * STRATA + \beta_3 * TRT \end{aligned}$$

- KCCQ-TSS change from baseline at 16 Weeks:

$$\begin{aligned} E[CHG_{KCCQ-TSS} | BASE_{KCCQ-TSS}, TRT] \\ = \beta_0 + \beta_1 * BASE_{KCCQ-TSS} + \beta_2 * STRATA + \beta_3 * TRT \end{aligned}$$

Model summary in Part B

- 6MWD change from baseline at 24 Weeks:

$$\begin{aligned} E[CHG_{6MWD} | BASE_{6MWD}, TRT] \\ = \beta_0 + \beta_1 * BASE_{6MWD} + \beta_2 * STRATA + \beta_3 * TRT \end{aligned}$$

- KCCQ-TSS change from baseline at 24 Weeks:

$$\begin{aligned} E[CHG_{KCCQ-TSS} | BASE_{KCCQ-TSS}, TRT] \\ = \beta_0 + \beta_1 * BASE_{KCCQ-TSS} + \beta_2 * STRATA + \beta_3 * TRT + \beta_4 \\ * BASE_{KCCQ-TSS} * TRT \end{aligned}$$

Where TRT indicates randomized treatment group; STRATA indicates neutrophil baseline strata; BASE_{6MWD} and CHG_{6MWD} indicates baseline and change from baseline in 6MWD, respectively; and BASE_{KCCQ-TSS} and CHG_{KCCQ-TSS} indicates baseline and change from baseline in KCCQ-TSS, respectively.

Subgroup analyses will be performed for both primary endpoints.

Primary Efficacy Objectives Related Estimands:

Part A:

Treatment: Treatment with 2.5 mg or 5 mg AZD4831 compared to placebo, administered in addition to optimal back-ground therapy for co-morbidities.

Population: Patients that fulfill all of the inclusion criteria, none of the exclusion criteria and have available measurements of the efficacy endpoint at baseline and 16 weeks.

Endpoint: Change from baseline to 16 weeks in KCCQ-TSS and 6MWD.

Intercurrent events: Patients with intercurrent events resulting in missing assessments of the primary endpoints, eg, terminal events or withdrawal from the study, is expected to be very few and will be excluded from the analysis (principal stratum strategy). Other intercurrent

events, eg, premature discontinuation of study treatment, will be ignored (treatment policy strategy).

Population-level summary: Difference in adjusted mean change from baseline between groups.

Missing data will not be imputed.

Part B:

Treatment: Treatment with either 2.5 mg or 5 mg AZD4831 compared to placebo, administered in addition to optimal back-ground therapy for co-morbidities.

Population: Patients that fulfill all of the inclusion and none of the exclusion criteria.

Endpoint: Change from baseline to 24 weeks in KCCQ-TSS and 6MWD.

Intercurrent events:

- Deaths will be handled by a While-alive strategy, implemented by using the change from baseline to 24 weeks or last measurement prior to death (if earlier than 24 weeks).
- Intercurrent events other than deaths will be handled by a Treatment-policy strategy, ie, measurements will be collected and used in the statistical analysis regardless of the occurrence of the event

Population-level summary: Between group difference in mean change from baseline at 24 weeks or prior to death, if earlier. For KCCQ-TSS, this will be a function of baseline values.

For patients with missing measurements for reasons other than death, a multiple imputation scheme will be employed, which differentiates between monotonous and non-monotonous missing data. Monotonous missing data are where observations are consistently missing after a point in time whereas non-monotonous missing data are missing observations followed by at least one recorded observation. For monotonous missing data, retrieved dropouts (patients remaining in the study despite same intercurrent events as drop-outs) will be used to impute missing values or, if there are too few retrieved dropouts, a Jump-to-reference approach utilizing placebo patients will be applied.

As a supplementary approach, analyses where deaths are combined with the outcome variables in a Composite strategy will be conducted, and will be described in the SAP for Part B.

Methods for multiplicity control, both Part A and Part B:

The endpoints will be tested using an overall 2-sided alpha level of 0.05. Multiplicity across primary and secondary endpoints will be accounted for by utilising a pre-specified testing

procedure of the primary and secondary endpoints (and potentially among doses in Part A) and alpha recycling will be considered using a weighted group sequential recycling procedure following the approach of Burman et al (2009), (Ye et al 2013). Details will be described in the SAPs.

9.4.2.2 Secondary Endpoint(s)

The secondary efficacy endpoints for Part A are 6MWD and KCCQ-TSS (at 24 and 48 weeks), NT-proBNP, IL-6, and hsCRP (at 16, 24, and 48 weeks), LV-GLS, LAVI, and LVMI (at 16 and 24 weeks), and pharmacokinetic concentrations. The secondary efficacy endpoints for Part B are NT-proBNP, IL-6, and hsCRP (at 24 weeks). The secondary efficacy variables will be change from baseline in 6MWD, LV-GLS, LAVI, and LVMI for Part A and NT-proBNP, IL-6, and hsCRP for Parts A and B, and will be analysed in the same manner as for the primary endpoint of 6MWD. The secondary efficacy variable of KCCQ-TSS will be analysed in the same manner as for the primary endpoint of KCCQ-TSS. NT-proBNP, IL-6, and hsCRP will be analysed by applying log scale.

Plasma concentrations of AZD4831 will be summarised by timepoints and dose level. If PK data permit, PK parameters, eg, AUC and C_{max} , will be derived but also a population PK model will be developed, possibly with the support of PK data from other studies, using nonlinear mixed effects regression analysis in NONMEM. Furthermore, if data allows, the population PK model may be coupled with separate PD models. All PK/PD modelling will be described in a separate data analysis plan. Moreover, the derived PK parameters and the results of any such modelling will be provided in a separate PK and population PK/PD report (as an appendix to the CSR or as a stand-alone report).

9.4.2.3 Tertiary/Exploratory Endpoint(s)

Tertiary/exploratory endpoints will be described in the SAPs.

9.4.3 Safety

Safety and tolerability will be evaluated in terms of AEs, Vital signs, Clinical laboratory variables, and ECG. In addition, extra evaluation will be done for the following Adverse Events of Special Interest (AEoSI): skin reactions, including maculopapular rash, and infections (see Section 8.2). Exposure to study treatment will be described.

Safety analyses will be performed using the safety analysis set in Part A, and using the full analysis set in Part B. Safety data will be presented using descriptive statistics unless otherwise specified.

Safety analyses will be performed for two different study periods: on-study and on-treatment. These periods are defined in the Part A SAP and Part B SAP, respectively.

Safety Estimand Definition

The aim with the analyses of safety data is to assess the general safety objective, evaluated in a scenario where study treatment is not prematurely discontinued. Two analysis approaches are considered complementary to assess this hypothetical scenario for all safety endpoints:

- On-treatment; unbiased under the assumption that censoring following premature treatment discontinuation is non-informative.
- On-study; unbiased under the assumption that the risk for an event is independent of continued treatment. Note that this approach could also be described as handling premature treatment discontinuation with a treatment policy approach.

Hence, the general safety objective will be assessed through an estimand defined by the following attributes:

Population: Patients that fulfill all of the inclusion and none of the exclusion criteria..

Treatment: Treatment with either 2.5 mg or 5 mg of AZD4831 compared to placebo, administered in addition to optimal back-ground therapy for co-morbidities.

Intercurrent events:

- Premature study treatment discontinuation: All analyses will be provided using two complementary approaches.
 - Hypothetical as premature study treatment discontinuation cannot occur, implemented by excluding/censoring data after premature study treatment discontinuation + 14 days.
 - Treatment policy by ignoring study treatment discontinuation, implemented by including all available data.
- Initiation or change of concomitant medication, including rescue medication: Will be ignored, that is, handled using a treatment policy approach.
- Death: With the exception of assessment of mortality, will be handled hypothetically as it cannot occur, implemented by censoring time to event data at death and not imputing any data after death.

Population level summaries: Distribution of endpoints by treatment group, Kaplan-Meier estimate for endpoints by treatment group, difference in Kaplan-Meier estimates between treatment groups and treatment hazard ratios.

This estimand requires that to the extent possible, randomised subjects are followed up regardless of study intervention compliance and adherence to the study protocol.

Adverse Events

All AEs will be classified by system organ class, high level group term, high level term, and preferred term according to MedDRA.

AEs will be presented for each treatment group by SOC and/or PT, covering number and percentage of subjects reporting at least one event. An overview of AEs will present for each treatment group the number and percentage of subjects with any AE, AEs with outcome of death, serious AEs, and AEs leading to discontinuation of IP. Separate AE tables will be provided taking into consideration seriousness, death, and events leading to discontinuation of IP. An additional table will present number and percentage of subjects with most common AEs. Most common (eg, frequency of $>x\%$, $\geq x\%$) will be defined in the SAP. In accordance with the requirements of the FDA, a separate table will present non-serious AEs occurring in more than 5% of subjects in any treatment group. Key subject information will be presented for subjects with AEs with outcome of death, serious AEs, and AEs leading to discontinuation of IP. An AE listing for the safety analysis set will cover details for each individual AE. AEoSIs related to skin reactions, including maculopapular rash, and infection will be presented. Full details of AE analyses will be provided in the SAP.

All safety analyses are descriptive; hence no p-values will be presented for any safety analyses, and confidence intervals are provided as an illustration of precision of the estimate. Hazard ratio between treatment groups will be based on a Cox proportional hazards regression model with a factor for treatment group.

Treatment emergent

For Part A, the definition for treatment emergent events will be provided in the SAP.

For Part B, the following AEs are considered treatment emergent: AEs with an onset date on or after baseline or a worsening of pre-existing AEs on or after baseline. A treatment emergent abnormality is defined as a switch in a safety parameter from not-abnormal at baseline to abnormal at post-baseline assessments accordingly to predefined criteria specified in the SAP.

Vital signs

Vital sign parameters will be presented for each treatment group. Summary statistics for continuous variables cover n, mean, SD, Min, Q1, median, Q3, and Max. For each scheduled post-baseline visit, descriptive statistics for all vital sign parameters will be presented for observed values and change from baseline. Details of vital sign analyses will be provided in the SAP.

In Part B, time to first treatment emergent abnormality will also be presented.

Laboratory

Laboratory parameters will be presented for each treatment group. Summary statistics for continuous variables cover n, mean, SD, Min, Q1, median, Q3, and Max. For each scheduled post-baseline visit, descriptive statistics for all clinical chemistry and haematology parameters will be presented for observed values and change from baseline. A frequency table presents number of subjects reporting at least one treatment emergent change in selected laboratory parameters. Details of laboratory analyses will be provided in the SAP.

In Part B, time to first treatment emergent abnormality will also be presented.

Electrocardiogram

Electrocardiogram evaluation will be summarised and presented by treatment group for baseline and for each scheduled post-baseline assessment. More details of ECG analyses will be provided in the SAP.

